3 STUDY DESIGN

3.1 Description of the Study Design ([Figure 1](#))

The trial is a randomized double-blind placebo-controlled study to examine the effect of single infusions of VRC01 and 10-1074 in HIV-infected individuals undergoing sequential antiretroviral treatment interruptions. Participants will be randomized 1:1 to treatment with VRC01 plus 10-1074 or normal saline placebo. Study staff and participants will be blinded to treatment assignments.

First ATI

The day following study enrollment, subjects will stop ART (Day 0). Subjects taking non-nucleoside reverse transcriptase inhibitors (NNRTIs) will switch to a protease or integrase inhibitor-based regimen at least 2 weeks prior to Day 0 to ensure that the washout period of antiretroviral agents is roughly equal. During this first ATI phase of the study, HIV ribonucleic acid (RNA) levels and CD4⁺ T cell counts will be monitored every 2 weeks until plasma viremia of ≥ 200 copies/mL is detected.

VRC01 plus 10-1074/ Placebo Treatment Phase

Within 14 days of the first reported plasma viremia value of ≥ 200 copies/mL, subjects will be randomized 1:1 to receive single sequential infusions of VRC01 and 10-1074 or 2 sequential infusions of saline placebo. All subjects will restart ART the day following their bNAb/placebo infusions.

Second ATI

After re-institution of ART, subjects will have plasma viremia measured every 4 weeks. Twelve weeks after achieving ART-induced viral suppression subjects will undergo a second analytical treatment interruption. Viral suppression is defined as a plasma viremia < 40 copies/mL.

Transient “blips” in plasma viral levels are allowed as long as blips are < 400 copies/mL and succeeding viral levels return to < 40 copies/mL on subsequent testing.

[figure not shown]
During this second ATI, plasma viremia and CD4⁺ T cell counts will be monitored every 2 weeks and subjects will restart ART if they meet one or more of the following criteria prior to reaching ATI week 16:

- A confirmed $> 30\%$ decline in baseline CD4⁺ T cell count or an absolute CD4⁺ T cell count < 350 cells/mm³ that is associated with a HIV RNA level > 40 copies/mL.

- A sustained (>4 weeks) HIV RNA level of >1,000 copies/mL
- Any HIV-related syndrome (e.g. acute retroviral syndrome, opportunistic infection)
- Pregnancy

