6.3 First ATI Phase

The day following the enrollment visit, the participants will be instructed to stop their ART.

Storage of plasma, serum, and cells may be done at ATI Week 2, 4 and every 2 weeks thereafter for the duration of the first ATI phase. Flow cytometry (including CD4 count) and plasma HIV viral RNA levels will be done every 2 weeks for the duration of the ATI Phase. HIV genotype will be obtained on all samples with HIV viral levels >1,000 copies/mL. For select participants residing outside the local (Bethesda, MD) area, blood samples for blood draw only visits, may be collected at their local clinics or Quest Diagnostics and sent to the NIH CC for

testing. Samples collected at clinics or at Quest may be labeled with a coded identifier, gender, and date of birth, as required by the local facility.

During the first ATI Phase, participants will be evaluated at the CC outpatient clinic every 4 weeks. At these clinic visits, the following will be done in addition to the flow cytometry panel and plasma HIV viral level:

- Interval medical history and a targeted physical examination, including weight, vital signs, and a symptom-directed evaluation based on symptoms or complaints reported by each subject
- Assessment of concomitant medications
- Assessment of any new or unresolved AEs/intercurrent illnesses
- Blood collection:
 - CBC with differential
 - Chemistry panels, to include: ALT, AST, ALP, creatinine, total and direct bilirubin, and serum albumin levels
 - HIV transmission risk behavior assessment and counseling

For participants who are unable to return to the NIH CC during the COVID-19 pandemic/epidemic due to travel restrictions, blood samples may be collected at their local clinics or Quest Diagnostics and sent to the NIH CC for testing which will include; CBC with differential, plasma HIV viral level, and flow cytometry. Chemistry panels may be collected and run at Quest Diagnostics laboratories with results sent to the NIH. A study provider (Nurse Practitioner, Physician's Assistant, or Physician) will contact participants by phone and obtain an interval medical history.

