6.4 Treatment Phase

When a single plasma viral level that is ≥ 200 copies/mL is detected, the participant will return within 14 days for randomization and entry into the Treatment Phase of the study. Following randomization, participants will receive single infusions of 10-1074/placebo and VRC01/placebo given sequentially at the same visit. All participants will be instructed to restart ART the day following study infusions. Participants will be contacted by phone 72 hours after the study infusions to verbally assess for any reactogenicity symptoms (e.g. rash, arthalgias, fever).

During the Treatment Phase of the study, participants will be seen on the day of bNAb/placebo infusion and every 4 weeks thereafter and undergo the following study procedures.

- Interval medical history and a targeted physical examination, including weight, vital signs, and a symptom-directed evaluation based on symptoms or complaints reported by each subject
- Assessment of any new or unresolved AEs or intercurrent illnesses
- Blood collection for:
 - CBC with differential
 - Chemistry panels, to include: ALT, AST, ALP, creatinine, total and direct bilirubin, and serum albumin levels
 - Plasma HIV viral level
 - Flow cytometry panel
 - Storage of serum, plasma and PBMCs

- Serum or urine pregnancy test for women of child-bearing potential (at infusion visit only)

For participants who are unable to return to the NIH CC during the COVID-19 pandemic/epidemic due to travel restrictions, blood samples may be collected at their local clinics or Quest Diagnostics and sent to the NIH CC for testing which will include; CBC with differential, plasma HIV viral level, and flow cytometry. Chemistry panels may be collected and run at Quest Diagnostics Laboratories with results sent to the NIH. A study provider (Nurse Practitioner, Physician's Assistant, or Physician) will contact participants by phone and obtain an interval medical history.

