14 STATISTICAL CONSIDERATIONS

Efficacy Analysis

The primary outcome is the time from the start of the second treatment interruption until the subject meets criteria to restart ART. The probabilities of remaining below restart criteria for different amounts of time will be displayed using Kaplan-Meier plots and compared using the log-rank test. Secondary analyses will compare time to other milestones such as VL>400 and VL>1,000.

Safety Analysis

The proportion of subjects with grade 3 or higher AEs will be computed in each arm, along with 95% exact confidence intervals using the Clopper/Pearson method. The between-arm difference in the proportion of subjects with an AE of grade 3 or higher will be compared using Fisher's exact test and its associated confidence interval obtained by inverting two 1-sided tests at alpha=0.025.

Sample Size

Using control data from another similar trial, we modeled the time T (in days) to meet restart criteria as a Weibull distribution with survival function $P(T>t)=\exp[-(\lambda t)^p]$, where $\lambda=\exp(-3.861)=0.021$ and $p=1.957$. From these parameters, we estimated the median time to meet restart criteria as 39.486 days in the control arm. We can express the treatment effect in terms of either the hazard ratio θ or the factor β by which treatment increases the median time to meet restart criteria; β and θ are related by $\beta=\theta^{-1/p}$.

Assuming 25 subjects per arm are followed for 180 days, nearly everyone in both arms would be expected to meet restart criteria by 180 days. Power for a 40%, 50%, and 60% reduction in hazard is approximately 44%, 69%, and 90%, respectively ([Table 2](#)). These hazard reductions correspond to 30%, 42.5%, and 60% increases in the median time to meet restart criteria. Therefore, power is approximately 90% if the bNAb increases the median time to meet restart criteria by 60% relative to the placebo arm.

Table 2. Power under different treatment effects, expressed as either reduction in hazard or percent increase in median time to meet restart criteria.

Reduction in hazard	% Increase in median time to meet restart criteria	Power
40%	30%	44%
50%	42.5%	69%
60%	60%	90%

In terms of safety, a sample size of 25 subjects in the bNAb arm provides approximately 93% probability of detecting at least one AE that occurs in 10% or more of the population.

Table 3. Probability that at least 1 of 25 people in the bNAb arm will experience an AE that occurs in at least 10% of the population.

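### The primary log-rank test makes no use of each randomised participant's first-ATI rebound time, a baseline value that could add power if it predicts the second-ATI endpoint

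*Combined protocol and SAP*

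**What the plan says.** Section 14 (Efficacy Analysis) defines the endpoint: "The primary outcome is the time from the start of the second treatment interruption until the subject meets criteria to restart ART". The probabilities of not yet meeting the criteria "will be displayed using Kaplan-Meier plots and compared using the log-rank test". The only other efficacy analyses change the milestone: "Secondary analyses will compare time to other milestones such as VL>400 and VL>1,000". No covariate, stratification factor or adjusted analysis is named. Sections 3.1 and 6.4 describe 1:1 randomisation without a stratification factor.

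The order of events matters here. ART stops on Day 0. Under Section 3.1, HIV RNA and CD4 counts in the first ATI "will be monitored every 2 weeks until plasma viremia of ≥ 200 copies/mL is detected". Section 6.4 then says: "When a single plasma viral level that is ≥ 200 copies/mL is detected, the participant will return within 14 days for randomization". The time from Day 0 to that first value is therefore recorded before allocation.

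The second-ATI endpoint is not the same event. Its main viral criterion in Section 3.1 is "A sustained (>4 weeks) HIV RNA level of >1,000 copies/mL". A CD4 decline, an HIV-related syndrome or pregnancy also counts.

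**The concern.** The sequential design takes each participant through an off-ART run before allocation. The first-ATI rebound time cannot be affected by treatment. It exists, uncensored, for every randomised participant, because anyone who never reaches 200 copies/mL is not randomised. It needs no further visit or assay. If fast rebounders in the first ATI tend to be fast in the second, an unadjusted comparison leaves that between-person variation in the noise. Nor does anything in the design or analysis deal with a chance imbalance of fast and slow rebounders at 25 per arm.

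What is at stake is power. The plan states 44% and 69% for 40% and 50% hazard reductions, so a few points recovered from data already in hand would be useful.

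**Working it through.** **Inputs from Section 14.** 25 per arm; 180 days of follow-up with nearly everyone meeting the criteria, so about 50 events; control Weibull with λ = exp(−3.861) = 0.021 and p = 1.957; hazard ratios 0.6, 0.5 and 0.4. The efficacy alpha is not stated. I assume two-sided 0.05 because it reproduces Table 2.

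**Step 1: the plan's own figures.** Power = Φ(|ln HR| × √(50/4) − 1.96), with √12.5 = 3.536.
- HR 0.6: 0.511 × 3.536 − 1.96 = −0.154, giving 43.9% (plan 44%).
- HR 0.5: 0.693 × 3.536 − 1.96 = 0.491, giving 68.8% (plan 69%).
- HR 0.4: 0.916 × 3.536 − 1.96 = 1.280, giving 90.0% (plan 90%).

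The median ratios θ^(−1/p) are 1.298, 1.425 and 1.597, matching the stated 30%, 42.5% and 60%. Table 2 reproduces.

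**Step 2: what adjustment could add.** Second-ATI times came from the plan's Weibull. First-ATI times were linked to them by a Gaussian copula with an assumed correlation, because the documents give none. Both times were rounded up to 14-day visits. The adjusted test regresses the log-rank scores on treatment and log first-ATI time. With 8,000 simulated trials per cell, the simulation error is at most √(0.25/8,000) = 0.6 points. In this run the first-ATI scale was set at 0.6 of the second-ATI scale, also an assumption. Power (%) is shown for 40/50/60% hazard reductions:

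| Assumed correlation | Planned log-rank | Adjusted scores (t-test) | Change (points) |
|---|---|---|---|
| 0 | 40.8 / 64.5 / 86.3 | 38.7 / 61.6 / 84.2 | −2.1 / −2.9 / −2.1 |
| 0.3 | 41.0 / 64.3 / 85.8 | 40.9 / 64.3 / 86.2 | −0.1 / 0.0 / +0.4 |
| 0.5 | 40.1 / 64.0 / 85.9 | 44.9 / 70.4 / 91.1 | +4.8 / +6.4 / +5.2 |
| 0.7 | 39.8 / 64.0 / 86.3 | 54.2 / 81.0 / 95.8 | +14.4 / +17.0 / +9.5 |

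After rounding to the visit grid, the correlation of the log times falls from 0.3, 0.5 and 0.7 to about 0.26, 0.45 and 0.63. The gain survives that coarsening. Simulated log-rank power sits a few points below Table 2, so each comparison above is simulated against simulated.

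**Step 3: the same scores with a re-randomisation p-value, 14-day grid, cut at week 16.**
- Correlation 0.5: 41/65/86% becomes 46/71/90%, that is +5/+6/+4.
- Correlation 0.7: 40/64/86% becomes 54/80/96%, that is +14/+16/+10.
- Correlation 0.3: no gain. Correlation 0: a loss of about 2 points.

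**Step 4: level of the candidate tests.** Type I error was 4.4–5.9% for the re-randomisation test (simulation error 0.4 points) and 4.6–5.1% for the t-test on adjusted scores. A plain Cox model with the covariate ran at about 5–7.5%, and a Cox score test on the visit grid at 6.5–6.8%. Part of any power gain quoted for those Cox tests would come from a looser test. Stratifying the log-rank test at the median first-ATI time recovered less: about 1–2 points at correlation 0.5 and 6–9 at 0.7.

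**The case against.** The strongest reply is that nothing here is an error. The log-rank test is valid, Table 2 is right for it, and the Protocol Summary calls the trial exploratory and Phase 1. That stands.

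A reader might infer that the planned analysis is biased, that Table 2 overstates power because of it, or that power is certainly being wasted. The documents support none of these. The test is unbiased without the covariate. Whether any power is lost depends on a correlation that the documents do not give. At 0.3 there is nothing to gain, and at 0 the adjusted test loses slightly. Part of that loss reflects the log-rank test's own mild small-sample liberality: its simulated level on the visit grid was 4.8–6.0%.

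A reader might also treat the first-ATI time as an earlier measurement of the same outcome. It is not. It is a single value at a lower threshold, whereas the endpoint requires sustained viraemia above a higher one or a non-virological criterion, and pregnancy is not rebound at all. A covariate need only be prognostic, so validity is unaffected, but the difference could hold the correlation down.

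Finally, the change is more than one sentence in Section 14. The futility rule is built on the conditional probability of a significant final result, with a 30% threshold and a stated interpretation. A new primary test alters that calculation.

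What remains is that a complete, pre-randomisation, plausibly prognostic value is collected and not used, and that using it risks little.

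**Conclusion.** The point holds as a modest and conditional efficiency improvement. Measured against the planned log-rank test, a level-holding adjusted test changes power by about −2 points at correlation 0, about 0 at 0.3, +4 to +6 at 0.5 and +10 to +16 at 0.7. These figures rest on the plan's Weibull, a Gaussian copula, assumed first-ATI times and two-sided 0.05. The correlation is the decisive assumption and is unknown. The case for changing is the asymmetry: a small loss if the first-ATI time is uninformative, against a material gain if it is moderately or strongly prognostic, in the range of effects where stated power is weakest.

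**What to change.** Before any unblinded look, including the halfway futility analysis, amend Section 14 to name one primary test: log-rank scores adjusted for the log of time from Day 0 to first HIV RNA ≥200 copies/mL in the first ATI, with a re-randomisation p-value generated under the allocation scheme actually used. Fix the log transformation in advance. Do not substitute a plain Cox Wald or score p-value, and do not leave a choice between p-values. Keep the Kaplan-Meier plot and the unadjusted log-rank test as supportive. Compute the conditional power under the Futility heading of Section 14 with the same adjusted test, and recheck the stated meaning of the 30% threshold.

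The change needs no new participants, visits or assays. It costs about 2 points of power if the first-ATI time carries no information, and the futility calculation must be redone. If a Cox estimate is reported alongside, its hazard ratio is conditional on first-ATI time and should be labelled so, because the plan expresses effects without conditioning on it.

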10-1074 was evaluated in a Phase 1 study in both HIV-uninfected and HIV-infected individuals (protocol MCA-885). Study subjects were administered one IV infusion of 10-1074 at increasing dose levels (3 mg/kg, 10 mg/kg or 30 mg/kg) and were followed for 24 weeks after infusion.

A total of 33 study subjects enrolled in the study (14 HIV-uninfected and 16 viremic and 3 ART-treated HIV-infected individuals) received 10-1074. Of these, 21 received one infusion of 30 mg/kg. 10-1074 was generally safe and well-tolerated. A total of 57 AEs was reported during a follow-up period of 6 months, 88% of these were of grade 1 severity. The most commonly reported AE deemed possibly related to the study drug was transient, mild headache. There were no SAEs or grade 3 related AEs. A safety data summary is included in the 10-1074 IB.

Thirteen viremic subjects received 10-1074 at 30 mg/kg. Eleven of these subjects had pre-therapy viral isolates sensitive to 10-1074 *in vitro* and showed a rapid decline in viremia by a mean of 1.52 log₁₀ copies/mL. Virologic analysis revealed the emergence of 10-1074-resistant viruses in the first weeks after infusion. Emerging escape variants carried mutations in known contact sites (N332, N334 and D/N425) and were generally resistant to the related V3-specific antibody PGT121, but remained sensitive to antibodies targeting non-overlapping epitopes, such as the anti-CD4-binding-site antibodies, 3BNC117 and VRC01²².

1.1.3.3 10-1074 used in combination with 3BNC117

Two Phase 1 clinical trials of the combination of 3BNC117 (a bNAb that, like VRC01, recognizes the CD4 binding site on gp120) plus 10-1074 are currently underway. In one study (protocol YCO-0899), HIV-uninfected individuals received 1-3 doses of the antibody combination at 3 or 10 mg/kg versus placebo administered intravenously. Twenty-four subjects are enrolled, and all antibody infusions have been administered. Follow-up is ongoing and study assignment remains blinded.

In the second study (protocol MCA-0906), HIV-infected individuals on or off ART received 1 to 3 doses of 3BNC117 plus 10-1074 at 10 or 30 mg/kg each or placebo. To date, 29 individuals enrolled (25 received the antibody combination and 4 received placebo) in this study; 8 have received 3 infusions of 30 mg/kg, administered 3 weeks apart.

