3.2.2 Secondary Endpoints

The rate of occurrence of grade 3 or higher AEs, including SAEs, that, per standard criteria (see safety [Section 12.3.1](#)) are probably or definitely related to the test articles VRC01 and 10-1074.

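### Cheap improvement: at 25 per arm, Boschloo's exact test with a matching interval would give more power than Fisher's test for the safety comparison, with type I error still below 5%

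*Combined protocol and SAP*

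**What the plan says.** The Safety Analysis in Section 14 reports, for each arm, the proportion of subjects with a grade 3 or higher AE, "along with 95% exact confidence intervals using the Clopper/Pearson method". It then says: "The between-arm difference in the proportion of subjects with an AE of grade 3 or higher will be compared using Fisher's exact test", and adds "its associated confidence interval obtained by inverting two 1-sided tests at alpha=0.025". This is the only between-arm hypothesis test planned for safety.

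The plan gives no significance level for the p-value itself, and no size or power for the test. Its one safety operating figure concerns a single arm: "a sample size of 25 subjects in the bNAb arm provides approximately 93% probability of detecting at least one AE" when the AE frequency is 10% or more (Table 3 adds 1% and 5%). The arm size comes from the same section ("Assuming 25 subjects per arm are followed for 180 days") and the allocation from Section 3.1 ("Participants will be randomized 1:1 to treatment with VRC01 plus 10-1074 or normal saline placebo").

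**The concern.** Fisher's test conditions on the total number of events. With 25 per arm and few events, only a handful of tables are possible for a given total, so the attainable p-values are far apart and the true type I error falls well below the nominal 5%. An unconditional exact test that ranks tables by the Fisher p-value (Boschloo's test) recovers part of that loss and still bounds the error at 5% for every common rate.

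What is at stake is efficiency in the one formal between-arm safety comparison, which serves the trial's only secondary objective. An excess of 5 of 25 on the antibodies against 0 of 25 on placebo would be reported as not significant under the planned test and as significant under the alternative, with no extra subject.

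**Working it through.** **Inputs.** 25 per arm, 1:1 (Sections 14 and 3.1). Level: two-sided 5%, an assumption taken from the two 1-sided tests at 0.025 stated for the interval. Background rate of grade 3 or higher AEs: not given, so a range is shown. Related events look rare in the earlier data; for 10-1074, Section 1.1.3 reports "There were no SAEs or grade 3 related AEs".

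**The plan's own safety figure.** 1 − (1 − p)^25 gives 22.2%, 72.3% and 92.8% at p = 1%, 5% and 10%. Table 3 (22%, 72%, 93%) reproduces. It describes the chance of seeing one event in one arm, not of detecting a difference.

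**Method.** All 26 × 26 outcomes were enumerated.
- Fisher: the two-sided p-value for each table. The minimum-likelihood and doubled one-sided versions give the same rejection region here.
- Boschloo: p = the maximum, over the common rate, of P(Fisher p ≤ observed Fisher p).
- Size and power: sums of products of binomial probabilities over the rejected tables.

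**One table by hand.** For 5 v 0, the one-sided Fisher p is C(25,5)/C(50,5) = 53,130/2,118,760 = 0.0251. Two-sided it is 0.0502, just above 5%.

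**Selected tables (events of 25 v 25).**

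| Table | Fisher p | Boschloo p |
|---|---|---|
| 4 v 0 | 0.110 | 0.065 |
| 5 v 0 | 0.0502 | 0.033 |
| 6 v 0 | 0.022 | 0.013 |
| 8 v 2 | 0.074 | 0.041 |
| 10 v 3 | 0.051 | 0.033 |
| 11 v 4 | 0.062 | 0.033 |

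Fisher rejects 362 tables and Boschloo 386. No table is rejected by Fisher alone. The 24 additional tables are 12 in each direction.

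**True size at nominal two-sided 5%.**

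| Common rate | Fisher | Boschloo |
|---|---|---|
| 4% | 0.03% | 0.2% |
| 5% | 0.08% | 0.4% |
| 10% | 0.9% | 1.9% |
| 20% | 2.2% | 3.8% |
| 30% | 2.3% | 4.5% |
| 40% | 3.0% | 4.4% |
| 50% | 3.3% | 3.7% |
| Maximum | 3.28% (at 50%) | 4.63% (at about 34%) |

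**Power over assumed true rates (antibody v placebo).**

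| Rates | Fisher | Boschloo |
|---|---|---|
| 5% v 1% | 0.1% | 0.6% |
| 10% v 4% | 1.6% | 4.0% |
| 10% v 2% | 2.3% | 6.2% |
| 20% v 4% | 23% | 31% |
| 20% v 2% | 30% | 43% |
| 40% v 10% | 59% | 69% |

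Because Boschloo's rejection region strictly contains Fisher's, its power is higher at every pair of rates strictly between 0 and 1.

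**The case against.** Fisher's test is valid and prespecified, and its error is on the conservative side. Choosing a conditional over an unconditional test is a legitimate preference, and this is a small exploratory phase 1 study with safety as a secondary objective. All of that stands, and it is why the point is an improvement and not an error.

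The gain is also small where events are rare. At the 1% to 10% frequencies used in Table 3, neither test has useful power, and Boschloo is itself far below 5%. The 5 v 0 case misses by only 0.0002, and under Boschloo the threshold simply moves, since 4 v 0 remains non-significant. That stands too, although 8 v 2 and 11 v 4 are not near-misses under Fisher and they also change.

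Two stronger readings are tempting. A reader might infer that Fisher's error rate here never exceeds about 2%. That holds only if the common rate is about 30% or less; the maximum is 3.3%. A reader might also infer that harm to participants would be missed. The documents do not support this. Under Section 12.8, one related SAE or grade 4 AE is a halting criterion, and related events of grade 3 or higher, apart from transient subjective infusion symptoms, are reviewed within 48 hours. The DSMB reviews safety unblinded (Sections 12.12 and 13.1). None of these uses the p-value, and the per-arm proportions and intervals would show 20% against 0% in any case.

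Finally, changing only the name of the test would leave the between-arm interval tied to Fisher's test. For 5 v 0, a Fisher-based interval could include no difference beside p=0.033. This objection is right, and the fix has to cover the interval.

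**Conclusion.** This is an optional, low-cost gain in efficiency. In the examples with an antibody-arm rate of 20% or more, power rises by about 8 to 12 percentage points (23% to 31%, 30% to 43%, 59% to 69%), and type I error stays at or below 4.63%. At rates of 10% or less on the antibodies the gain is at most about 4 points and power remains negligible.

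The figures rest on exactly 25 evaluable subjects per arm, a two-sided 5% level, and assumed event rates, because the documents give none. They apply to the outcome as Section 14 words it, all grade 3 or higher AEs. The secondary endpoint in Section 3.2.2 counts only those that "are probably or definitely related to the test articles VRC01 and 10-1074", which would be rarer and would put the comparison nearer the low-rate rows. That difference in definition is a separate matter to reconcile.

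**What to change.** In Section 14, Safety Analysis:
1. Replace Fisher's exact test with Boschloo's unconditional exact test, and state the level as two-sided 5%.
2. Replace the interval tied to Fisher's test with an exact unconditional interval for the difference in proportions, obtained by inverting two 1-sided tests at 0.025 with the same ordering, so that test and interval agree.
3. Keep the Clopper-Pearson interval in each arm.

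Make the change before unblinding, since choosing between tests after seeing a table such as 5 v 0 would not be credible. The cost is two short edits, with no added subjects or data collection, and the test is in standard software. The downsides are that it is less familiar to readers than Fisher's test and that the interval has to be respecified and checked.

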12.10 Replacement for Withdrawn Subjects

Any subject who withdraws from the study, or who discontinues the study agent, prematurely, and whose reasons for withdrawing from the study or discontinuing study agent administration are unrelated to any real or perceived effect of the study agent or their administration, may be replaced at the discretion of the PI.

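### The safety comparison names a difference in proportions, but the interval belonging to Fisher's test is for the odds ratio and has no upper limit when the placebo arm has no events

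*Combined protocol and SAP*

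**What the plan says.** Section 14 (Safety Analysis) plans two things. Each arm's proportion with a grade 3 or higher AE gets "95% exact confidence intervals using the Clopper/Pearson method". For the comparison between arms, the quantity named is "The between-arm difference in the proportion of subjects with an AE of grade 3 or higher". The method given for it is Fisher's "exact test and its associated confidence interval obtained by inverting two 1-sided tests at alpha=0.025".

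The paragraph does not say whether the between-arm interval is for a difference, a ratio or an odds ratio. It does not say which two-sided Fisher p-value is meant, or what is reported when an arm has no events. The planned size is 25 per arm (Section 14, Sample Size), with 1:1 allocation (Section 3.1). Some withdrawn subjects "may be replaced at the discretion of the PI" (Section 12.10), so the final arms need not be equal.

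**The concern.** The quantity named and the method named do not match. Fisher's test conditions on the total number of events. Given that total, the distribution of the bNAb-arm count depends on the two event rates only through their odds ratio. The interval that belongs to the test is therefore an odds-ratio interval, and no interval for the difference can be obtained from it.

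Two analysts following the sentence could report different quantities. One would give the conditional odds-ratio interval. The other would choose some exact interval for the difference, which is a separate procedure that the plan does not name. A safety reader wants to know how large an excess risk the data rule out. The odds-ratio interval cannot answer that when placebo has no events, because it then has no upper limit. This is also the only between-arm safety comparison that Section 14 specifies.

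**Working it through.** **Inputs.** 25 per arm, two one-sided tests at 0.025, and the grade 3+ proportion, all from Section 14. No event rate for all grade 3+ AEs appears in the documents, so rates below are assumptions.

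**The plan's own safety figures reproduce.** Table 3 uses 1 - (1 - p)^25. This gives 22.2%, 72.3% and 92.8% at p = 1%, 5% and 10%, against 22%, 72% and 93% stated. Section 14 gives no power or expected interval width for the between-arm comparison.

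**Odds-ratio interval from Fisher's test.** Take 2/25 bNAb v 0/25 placebo. Given 2 events in total, the bNAb count has weights C(25,2)ψ² = 300ψ², 25×25ψ = 625ψ and C(25,2) = 300, for 2, 1 and 0 events, where ψ is the odds ratio.
- Lower limit: 300ψ² / (300ψ² + 625ψ + 300) = 0.025. This becomes 292.5ψ² - 15.625ψ - 7.5 = 0, so ψ = 0.19.
- Upper limit: the observed count is the largest possible given the total, so P(X ≤ 2) = 1 for every ψ. No finite upper limit exists.

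**Exact unconditional score interval for the difference.** For each trial difference δ the statistic is (p̂1 - p̂0 - δ) / SE(δ), with SE(δ) from the maximum-likelihood rates constrained to differ by δ. Each one-sided p is maximised over the unknown common rate level. The interval keeps every δ not rejected by either test at 0.025 (grid of half a percentage point).

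| bNAb v placebo | Odds-ratio 95% CI (Fisher) | Difference 95% CI, points |
|---|---|---|
| 0/25 v 0/25 | 0 to infinity | -13.5 to +13.5 |
| 2/25 v 0/25 | 0.19 to infinity | -6.5 to +26 |
| 3/25 v 0/25 | 0.42 to infinity | -2.5 to +31 |
| 5/25 v 0/25 | 0.999 to infinity | +4.5 to +40.5 |
| 6/25 v 0/25 | 1.33 to infinity | +7.5 to +45 |
| 0/25 v 3/25 | 0 to 2.36 | -31 to +2.5 |

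The last row shows that an empty bNAb arm alone leaves a finite upper limit. The problem arises when placebo, or both arms, have no events.

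**How often an arm is empty.** Let z = (1 - r)^25 for a rate r assumed equal in both arms. At least one arm is empty with probability 1 - (1 - z)².

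| Rate r | Placebo empty (z) | At least one arm empty | Both empty (z²) |
|---|---|---|---|
| 2% | 60% | 84% | 36% |
| 5% | 28% | 48% | 8% |
| 10% | 7% | 14% | 0.5% |
| 15% | 2% | 3% | 0.03% |

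**Agreement between p-value and interval.** The interval inverts two one-sided 0.025 tests, so it matches a p-value equal to twice the smaller one-sided p. The usual software p-value instead sums the tables no more probable than the one observed. Comparing the two at 0.05 over all possible tables gives conflicts in:
- 25/25: 0 of 676
- 25/24: 20 of 650 (3.1%)
- 26/24: 16 of 675 (2.4%)
- 27/23: 20 of 672 (3.0%)

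Example: 4/24 v 0/26. The observed table has probability C(24,4)/C(50,4) = 10,626/230,300 = 0.0461. The opposite extreme has C(26,4)/C(50,4) = 14,950/230,300 = 0.0649, which is larger and so is not added. The usual p is therefore 0.046, twice the one-sided p is 0.092, and the odds-ratio interval is 0.76 to infinity.

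**The case against.** The strongest reply is that the sentence is underspecified rather than wrong. The difference is what is compared, and nothing expressly says that the interval is on the difference scale. Fisher's test with its conditional interval is a standard exact method. The per-arm Clopper-Pearson intervals already show absolute risk: for 0/25 the upper limit is 1 - 0.025^(1/25) = 13.7%, close to the +13.5 points for the difference at 0 v 0. Study halting under Section 12.8 is triggered by events, not by this interval.

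Much of this stands, and it keeps the point small. It does not remove the mismatch: the interval named is not for the quantity named, and per-arm intervals are not an interval for the excess.

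Four stronger readings might be inferred, and the documents do not support them.
- **That p-value and interval will contradict each other.** This needs the probability-ordered p-value, which the plan does not specify. Its wording "obtained by inverting two 1-sided tests at alpha=0.025" fits the central version, which cannot conflict at any arm sizes. No conflict is possible at 25/25 under either definition.
- **That exactly equal arms are unlikely.** That would assume simple randomisation. The plan says only 1:1 and does not describe the method.
- **That grade 3+ AEs will be sparse because earlier studies saw few.** The earlier counts (Sections 1.1.3.1 and 1.1.3.2) are of related events. This analysis counts all grade 3+ AEs, from the first infusion through follow-up (Section 12.3). The related-only endpoint in Section 3.2.2 would make empty arms more likely, but it is not what Section 14 analyses.
- **That Fisher's test must be abandoned.** It is a defensible test. What needs settling is the scale of the interval.

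**Conclusion.** The point holds as a mismatch between the effect measure and the interval method. Followed literally, Section 14 gives an odds-ratio interval that sets no upper bound on excess risk whenever placebo has no grade 3+ AE.

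How often that happens depends on a rate the documents do not give. With equal rates and 25 per arm, placebo is empty with probability 60% at 2%, 28% at 5% and 7% at 10%, so the problem largely disappears if grade 3+ AEs are common. The possible clash between p-value and interval is a side issue, limited to about 2-3% of tables at the near-equal splits checked and to one choice of p-value.

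Severity is minor: a secondary safety analysis in an exploratory Phase 1 trial, with per-arm intervals also planned.

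**What to change.** Change the sentence in Section 14 to say that the difference in proportions (bNAb minus placebo) will be reported with an exact unconditional 95% confidence interval, from inverting two one-sided 0.025 tests based on the score statistic. The statistic has to be named. For 6/25 v 0/25 the score version gives +7.5 to +45 points, while inverting the raw difference gives about -5 to +50, which includes 0 although Fisher's p is 0.022.

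If Fisher's test is kept, define its two-sided p as twice the smaller one-sided p and label any interval from it an odds-ratio interval. Say that an infinite limit will be reported as such when placebo has no events.

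The cost is one sentence and standard software. There is one downside. The unconditional interval and Fisher's p come from different tests and can differ. For 5/25 v 0/25, Fisher's p is 0.0502 while the difference interval is +4.5 to +40.5 points. For 4/23 v 0/25, twice the one-sided p is 0.091 while the interval is +2 to +38.5 points. The plan should therefore state, before unblinding, that the risk-difference interval is the main summary. Otherwise the choice between them could look data-driven.
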